Primary and Other Outcome Ascertainment: Primary outcome ascertainment of 30-day uptake of booster vaccine will occur in three ways:

- 1) Ascertainment of vaccination in the ED by direct questioning and review of EHR records.
- 2) Blinded review of EHR at 30-days
- 3) For participants who have not received a booster vaccine upon questioning in the ED, staff will ask whether they will agree to phone follow-up at 30 days. For those agreeing to follow-up, we will obtain written consent for phone follow-up (phone follow-up consent form). We will then ask participants for their best phone number(s) to reach them for a follow-up phone call. Sites will maintain a separate password protected database of subject IDs and follow-up phone numbers.

This method will assure that all study participants, even those who refuse phone follow-up, will have at least two ways of study outcome ascertainment (1 and 2 above).

[figure not shown]
Secondary outcome ascertainment of booster vaccination in the ED will occur in two ways:

- 1) Direct questioning of participants and their providers in the ED: Research staff will ask participants and their ED providers whether the participant received a booster vaccine in the ED one hour but up to 6-hours after the Vaccine Acceptance Survey. Notably, ED patient visits are variable such that not all patients have stays lasting greater than an hour and a half. Research staff should endeavor to complete this ascertainment prior to discharge, even if that ascertainment occurs before an hour after the Vaccine Acceptance survey.
- 2) Review of each participant's ED EHR by research staff on the next workday after their index ED visit to confirm receipt (or non-receipt) of a booster vaccine in the ED. **This EHR review will be conducted in a blinded fashion the research staff person reviewing the EHR will be unaware of participant's study group assignment.**

Procedures and workflow during PROBOOSTVAXED Intervention Q Study Arm

The workflow during this arm is identical to the Intervention M Arm except there will be no messaging platforms delivered. The anticipated flow of the study during **Intervention Q Blocks** is summarized in Figure 2.

Figure 2: Intervention Q Arm Study Flow

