CRCs will only review EHR and conduct phone follow-up with study subjects who have given written consent for these follow-up techniques. CRCs will check the EHR at two time periods — the day after their index visit and, if not vaccinated during their ED visit, again 30 days after their visit. CRCs will review Master Data Flow daily (workdays) to determine which subjects have reached the 1-month follow-up period. By convention, we will use the next month's day that has the same number as the index study visit date, i.e., if the study index visit was on November 5, then the 1-month follow-up should occur on December 5. If December 5 falls on a weekend, then the CRC will use the next study workday (typically the next Monday) as the follow-up date. Study subject's medical record #s and telephone #s will be accessed from the Booster Vaccine Follow Up sheet. The CRC who conducts EHR and phone follow-up will be blinded to the subject's study group assignment (intervention vs control arms), i.e., a separate CRC who did not recruit at that site during that day will conduct this phone follow up.

1) The CRC will first review the EHR to determine whether there is any record of a booster vaccine received in the preceding time period from the study index visit. If there is a record

- of vaccination, the CRC will record what date and where the participant received it (if available). See Follow-Up Data Collection form.
- 2) If there is no record of vaccination in the EHR, the CRC will proceed with a phone call to the study subject. See Follow-Up Phone Call Collection form. CRCs will enter follow up data on both the Master Data Flow and Follow up spreadsheets via REDCap links.
 - a. If the patient does not answer the phone that morning, the CRC will place two more calls to the study subject over the next 2 workdays. They will vary the time of these calls to improve response.
 - b. If the patient does not answer the phone by the third call, the CRC will leave a message with the phone # of the study team. No more calls will be initiated by the study team after this third call.

XIV. Data Recording and Entry

CRCs will record survey responses and other data via two mechanisms:

- 1) Direct entry into the Booster Vaccine Study REDCap database in real time during surveys via secure links
- 2) Recording onto paper forms first. Then entry of survey information and data after each participant enrollment.

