CRCs will keep a running log of all study flow and enrollment, recording the following data for all patients approached: study date, study arm, "Yes" and "No" agreeing to surveys, delivery or non-receipt of messaging platforms, agreeing to receipt of study vaccines, ED vaccine availability, receipt of vaccines in the ED, "Yes" and "No" agreeing to follow-up calls and EHR review. See Master Data Flow.

XV. Data Analysis Analysis for Specific Aim I

The primary study comparison is uptake (receipt) of a booster vaccine at any vaccination location within 30 days of the index ED visit, comparing participants seen on Intervention M dates with those seen on Control (No Messaging, No Vaccine Acceptance Question) dates to test our study hypothesis: *Implementation of PROBOOSTVAXED trusted messaging platforms in EDs will be associated with increased booster vaccine uptake in vaccinated ED patients*. This outcome will be ascertained by either review of a participant's EHR 30 days after their index ED visit or a follow-up phone call.

There are three secondary comparisons for Specific Aim I:

- 1) Comparison of 30-day booster vaccine uptake between the Intervention M and Intervention Q arms
- 2) Receipt of a booster vaccine during the index ED visit, comparing participants seen on Intervention M dates with those seen on Control dates - ascertained by check of the participant's EHR on the day after their ED visit

Outcomes will be compared using mixed logistic regression with a fixed effect for randomization assignment, a normally distributed random effect to allow for clustering by enrolling center, and restricted cubic splines to allow for secular trends during the study period. The treatment effects

will be tested by the coefficient for the fixed effect of study arm along with 95% confidence intervals.

Analysis for Specific Aim II

For Specific Aim II, we will compare outcomes in participants seen on Intervention M arm dates with those seen on Intervention Q arm dates to test our study hypothesis: *Implementation of PROBOOSTVAXED trusted messaging platforms in EDs will be associated with increased booster vaccine acceptance in vaccinated ED patients.*

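### Blinding of the 30-day follow-up is not fully protected by the workflow as written, and phone consent is sought after exposure to the intervention

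*Combined protocol and SAP*

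**What the plan says.** **Blinding.** Section XIII (30-Day Phone and EHR Follow Up) states: "The CRC who conducts EHR and phone follow-up will be blinded". The means given is that "a separate CRC who did not recruit at that site during that day will conduct this phone follow up". Contact details are held apart: "medical record #s and telephone #s will be accessed from the Booster Vaccine Follow Up sheet", and Section IX adds that "Sites will maintain a separate password protected database of subject IDs and follow-up phone numbers". Section XVI also keeps identifiers in files separate from other study data.

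The same part of Section XIII sets the daily routine: "CRCs will review Master Data Flow daily (workdays) to determine which subjects have reached the 1-month follow-up period", and later "CRCs will enter follow up data on both the Master Data Flow and Follow up spreadsheets via REDCap links". Section XIV describes the log and refers the reader to Master Data Flow: "CRCs will keep a running log of all study flow and enrollment, recording the following data for all patients approached: study date, study arm". Its listed contents also include "delivery or non-receipt of messaging platforms" and whether the participant agreed to follow-up calls and record review.

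**Phone consent.** Section IX (Primary and Other Outcome Ascertainment) has staff ask for phone follow-up, with its own written consent, only from participants found unvaccinated when questioned in the ED. That questioning is set one to six hours after the Vaccine Acceptance Survey, or sooner if discharge comes first. Record review at 30 days covers those who decline calls. Sections IX and X use the same ascertainment in the Q and Control arms. Section XIII counts a booster received anywhere.

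**The concern.** The promise of blinding and the described routine pull apart. Staff find who is due in a log that holds the allocation, and they enter results in that same log. No view without the arm, and no access limit, is described. The phone outcome is self-reported, so it can be affected by how a caller asks and records.

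The consent issue is separate. A participant who has just received messaging, or been asked to accept a vaccine, may be more or less willing to be called than a Control participant who has had neither. For a vaccination given after discharge and missing from the record, the call is the only route into the primary outcome. If willingness differs by arm, so does the chance of counting such a vaccination, and the M versus Control and Q versus Control comparisons of 30-day uptake absorb the difference.

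**Working it through.** **Blinding: the passages side by side.**
1. Section XIII: the person doing follow-up does not know the arm.
2. Section XIII: due participants are found in Master Data Flow, and results are entered in it.
3. Section XIV: that log holds study arm and messaging delivery.
4. Section V: a whole site-day has one arm, and the site opens its calendar that morning. Section XIII sets follow-up on the same day number of the next month, moved on if it falls on a weekend. The due date therefore points back to the index day, and the index day to the arm for anyone who saw the calendar.

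Keeping identifiers separate protects identity, not allocation. Using a different coordinator removes memory of recruitment but does not hide a field in the log. The documents give no basis for a numerical size here, so none is offered.

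**Consent timing: arithmetic.**

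*Inputs from Section XVII:* Control uptake 5%, target increase 7 points (so 12% in M), 248 per arm, alpha 0.05, power at least 0.80.

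*The plan's own figure.* With mean proportion 0.085 and a two-sided test:
n = [1.960 × √(2 × 0.085 × 0.915) + 0.842 × √(0.05 × 0.95 + 0.12 × 0.88)]² / 0.07² = 247.98, so 248 per arm and 3 × 248 = 744. This matches, and power at 248 is 80.0%.

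*Assumed inputs, not in the documents:* the record shows 30-70% of vaccinations; the phone captures 50-70% of the rest in Control; capture in M differs by 10-20 points either way; anyone not captured counts as unvaccinated. Capture here means consenting and answering combined.

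*No true effect (5% in both arms).* Spurious difference = 5% × (1 − record share) × capture gap.

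| Record share | Gap | Difference (points) | Share of 7 points | Participants per arm (× 248) |
|---|---|---|---|---|
| 70% | 0.10 | 5% × 0.3 × 0.10 = 0.15 | 2% | 0.37 |
| 50% | 0.20 | 5% × 0.5 × 0.20 = 0.50 | 7% | 1.24 |
| 30% | 0.20 | 5% × 0.7 × 0.20 = 0.70 | 10% | 1.74 |

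Type I error (normal approximation) is 5.1% for 0.15 points. For 0.50 points it is 5.8-5.9% if M is captured better and 5.9-6.1% if worse. For 0.70 points it is 6.7-7.0% and 7.0-7.5%. The worst case has record share 30%, Control capture 50% and M capture 30%: observed 5% × (0.3 + 0.7 × 0.5) = 3.25% against 5% × (0.3 + 0.7 × 0.3) = 2.55%, with rejection in 7.5% of trials.

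*Planned effect (12% against 5%).* Compared with equal capture, the observed difference moves by 12% × (1 − record share) × gap: from 12% × 0.3 × 0.10 = 0.36 points to 12% × 0.7 × 0.20 = 1.68 points, in either direction. That is 5% to 24% of the 7-point target; the upper end is the extreme corner of the assumed range.

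**The case against.** The strongest reply on blinding is that the plan commits to it and provides means. The sentence about reviewing the log speaks of coordinators in general and does not say that the blinded caller is the one who screens it. Section XIII names dedicated follow-up forms, and a REDCap link need not display other fields. The log layout, operations manual and data dictionary are not in the text. This stands to the extent that a reader who infers that follow-up is in fact unblinded goes beyond the documents. It does not remove the mismatch, because no text separates screening from calling and results go into the same log.

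On consent, restricting the request to those not vaccinated in the ED is not a bias in itself, since the others already have the outcome. Only the timing matters, and that is inferred from the sequence of steps; no sentence states it. Nothing in the documents suggests that refusal will differ by arm. The modelled gap also includes answering the call, which earlier consent cannot change. All of this stands.

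Two further inferences should be resisted. One is that every vaccination missing from the record depends on the call: direct questioning in the ED is also a listed route, so the point concerns vaccinations after discharge. The other is to count the power lost through equally incomplete capture in both arms. That is a different issue and does not measure this one.

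**Conclusion.** Both parts hold in limited form. The described workflow can expose the arm to the person recording the 30-day outcome, though the documents do not show that it would. Phone consent follows exposure, so capture of post-discharge vaccinations absent from the record could differ by arm.

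Size and direction are unknown. Under the assumptions above, the spurious difference with no true effect is 0.15-0.70 points (0.4-1.7 participants per arm) and the type I error at most about 7.5%. Record review for all participants, common procedures across arms and up to three call attempts limit the problem without removing it. Severity is minor to moderate; the case for acting rests on the low cost of the changes.

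**What to change.** 1. Give follow-up staff a daily call list and an entry form without arm, messaging or acceptance fields, and block their access to those fields in Master Data Flow. Because the due date reveals the index day, have follow-up done where feasible by existing staff who have not seen that site's allocation calendar. Cost: minor REDCap set-up and some rostering.
2. Obtain written consent for phone follow-up at enrolment, together with the HIPAA authorization and before messaging and the acceptance question, in all three arms. Participants who decline calls should remain in the study, as now. Cost: one more form for every participant, including the few later vaccinated in the ED.
3. Report phone-consent and phone-contact rates by arm, and add a sensitivity analysis of 30-day uptake using the health record alone. This is needed even with earlier consent, because answering the call may still differ by arm. Cost: one table, for which the log already holds arm and agreement to calls, and one extra model.

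None of these changes alters the intervention, the sample size or the primary analysis.

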Primary and Other Outcome Ascertainment: Primary outcome for Specific Aim I is booster vaccine uptake (at any vaccination location) within 30 days after participants' index ED visit, comparing the Intervention M arm versus the Control arm. For ascertainment of this outcome, we will:

- 1) Review the EHR the day after participants' index visit (as described for the secondary outcome ascertainment below).
- 2) Review the EHR at 30 days for receipt of a booster vaccine.

3) Conduct follow-up phone calls (*Have you received a booster vaccine since your emergency department visit?*) 30 days after index ED visits for those who did not get the vaccine in the ED and who consented to follow up.

Secondary outcome (vaccination in the ED) ascertainment will occur by review of each participant's ED EHR by research staff on the next workday after their index ED visit. Staff will check the EHR to confirm receipt (or non-receipt) of a booster vaccine in the ED. This review will be conducted in a blinded fashion – the research staff person reviewing the EHR will be unaware of participant's study group assignment.

Participants who have confirmed receipt by EHR review will be deemed "vaccinated in the ED". Conversely, participants who do not have confirmed receipt by review will be deemed to be "not vaccinated in the ED".

Outcome and Ascertainment of Specific Aim II

Our outcome for Specific Aim II is booster vaccine acceptance (defined as a response of "yes" to the question, "Would you accept the booster vaccine in the emergency department today if your doctor asked you?"), comparing the Intervention M arm versus Intervention Q arm. This outcome will be ascertained during the Vaccine Acceptance Survey in both arms.

Outcomes and Ascertainment of Specific Aim III

Our outcome for Specific Aim III is 30-day booster vaccine uptake (at any vaccination location), **comparing the** Intervention Q arm (Vaccine Acceptance Question, No Messaging) versus the Control arm (No Messaging, No Vaccine Acceptance Question). This outcome will be ascertained in the same manner as the primary outcome of Specific Aim I.

A secondary outcome for Specific Aim III is booster vaccination in the ED, comparing the Intervention Q arm versus the Control arm. This outcome will be ascertained in the same manner as the secondary outcome of Specific Aim I.

30-Day Phone and EHR Follow Up

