The sample size calculations for this research are governed by hypothesis testing of Specific Aim I -- Implementation of booster messaging platforms will be associated with increased booster vaccine uptake (primary outcome) in unvaccinated ED patients. Considering the high benefit of increasing vaccine uptake and the negligible risk of the intervention (a trusted messaging program), even a small effect size of increased uptake would be a clinically important difference. By investigator consensus, we have determined that the intervention would be clinically useful if it increased booster vaccine uptake by 7%.

We base the sample size calculation on the comparison of the proportion of patients who accept the vaccine between the Intervention M and Control time periods using standard formulae for individual randomization. We have verified that these sample sizes are conservative by simulation of data using a mixed random effects model. Our baseline level of vaccine uptake in the control arm is estimated to be approximately 5%. With this uptake level we find that at an alpha=0.05 level and a power of at least 0.80, we will need to enroll 744 participants (248 in each arm) in the study to detect the difference of interest (a setting in which the vaccine uptake rate will increase by 7% during Intervention periods vs Control periods).

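### A phone self-report counts toward 30-day uptake exactly as an EHR-recorded dose does, so over-reporting that is greater in Intervention M than in Control can inflate the primary difference without being seen

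*Combined protocol and SAP*

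**What the plan says.** - **Outcome rule.** Section XV (Analysis for Specific Aim I) takes 30-day uptake from review of the participant's "EHR 30 days after their index ED visit or a follow-up phone call". Either source is enough.
- **Who is called.** Section XIII (30-Day Phone and EHR Follow Up) has the coordinator read the EHR first. Then: "If there is no record of vaccination in the EHR, the CRC will proceed with a phone call to the study subject". Only those who gave written consent to phone follow-up are called, with at most three attempts.
- **What is asked.** Section XIII gives one self-report question, whether the participant has had a booster since the ED visit. For an EHR dose, date and place are to be recorded if available. For a phone dose the text points to a collection form that is not among the documents.
- **Blinding.** The coordinator doing the follow-up is blinded to arm. Nothing blinds the participant.
- **Exposure.** Sections IX and XII: only in Intervention M are participants offered a video and a flyer, and only there is the provider handed a script. Video and flyer may be declined, and research staff do not check whether the provider delivers the message.
- **Secondary outcome.** For vaccination in the ED, section XIII relies on the record: "Participants who have confirmed receipt by EHR review will be deemed" vaccinated in the ED, and those without such confirmation are not.
- **Analysis.** Section XV describes no coding by source, no check of phone answers and no analysis restricted to recorded doses.

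**The concern.** Phone-only positives are, by construction, doses for which the EHR showed nothing when the coordinator looked. Many may be real, because uptake counts at any location and only some study EDs will have vaccine. Some may be answers given to please. Caller blinding removes interviewer bias but not respondent bias, since participants know what they were shown.

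If the tendency to over-report is the same in both arms, it does little harm. If it is greater among people offered pro-vaccination messaging, it pushes the primary contrast toward benefit. Because both sources are merged into one yes/no variable, a positive Aim I result could not be separated into more vaccination and more reported vaccination. The same question arises in weaker form for Aim III, where Intervention Q participants are asked about acceptance and Control participants are not.

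Planned Control uptake is low, so a handful of answers matters.

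**Working it through.** **1. The plan's own figure.** Section XVII gives Control uptake of about 5%, an increase of 7 points (so 12%), alpha 0.05, power 0.80, "using standard formulae for individual randomization". With a two-sided test and pooled variance, mean proportion 0.085:

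n = [1.960·√(2·0.085·0.915) + 0.8416·√(0.05·0.95 + 0.12·0.88)]² / 0.07² = (0.7730 + 0.3293)² / 0.0049 = 248 per arm, and 3 × 248 = 744.

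This matches the plan and is unaffected by the point made here.

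**2. Scale.** Expected Control events: 0.05 × 248 = 12.4. One percentage point is 0.01 × 248 = 2.5 participants, so two or three false answers in one arm move the difference by about a point.

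**3. Bias with no true effect.** Inputs that the documents do not give, hence assumptions:
- share of participants with no record who are reached by phone: 40% or 60%;
- excess false positive answers in M over Control among them: 2 or 5 points;
- a factor of 0.9 for the share of those reached who truly had no dose. With 5% true uptake 0.95 would also be defensible, so 0.9 is the cautious choice.

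Bias = reach × excess × 0.9. The observed rates are then 5% and 5% + bias. The chance of a significant result in favour of M at 248 per arm is

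Φ{[d − 1.960·√(2p̄(1−p̄)/248)] / √[(p₁(1−p₁) + p₂(1−p₂))/248]}.

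The two-sided rate adds the opposite tail.

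| Reach | Excess in M | Bias (points) | Two-sided false-positive rate |
|---|---|---|---|
| 40% | 2 points | 0.4 × 2 × 0.9 = 0.72 | 6.5% |
| 60% | 2 points | 0.6 × 2 × 0.9 = 1.08 | 8.2% |
| 40% | 5 points | 0.4 × 5 × 0.9 = 1.80 | 13.6% |
| 60% | 5 points | 0.6 × 5 × 0.9 = 2.70 | 23.4% |

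Example, last row: d = 0.027, p̄ = 0.0635. The numerator is 0.0270 − 1.960 × 0.02190 = −0.0159, the denominator 0.02187, and Φ(−0.728) = 0.233. The opposite tail adds 0.0007.

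With 0.95 in place of 0.9, the bias runs from 0.8 to 2.9 points and the rate from 6.6% to 25.3%.

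**4. Equal over-reporting.** Under the null the difference stays at zero. With a true 5% against 12%, 60% reached and the same false rate in both arms:
- 2%: 0.05 + 0.95·0.6·0.02 = 0.0614 and 0.12 + 0.88·0.6·0.02 = 0.1306; difference 6.9 points, power 0.75.
- 5%: 0.0785 and 0.1464; difference 6.8 points, power 0.67.

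**5. How much would produce the whole planned effect?** 0.07/(0.95 × 0.6) = 12% excess false answers at 60% reach, and 0.07/(0.95 × 0.4) = 18% at 40%.

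**6. Cost of counting recorded doses only.** If the EHR captures 80% of true doses in both arms, the rates become 4.0% and 9.6% and power at 248 per arm is 0.70. At 60% capture they are 3.0% and 7.2%, with power 0.57.

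All of this ignores site clustering and the time splines.

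**The case against.** A reader might infer that over-reporting does inflate the result. The documents do not support that: they give no over-reporting rate and no evidence that it differs by arm. Several features also argue for a small differential. The caller is blinded, the question is neutral, and the call comes about a month after the visit. Video and flyer are optional and provider delivery is unchecked, so not everyone in M received all three messages. Control participants know the topic too, because their scripted consent names the Vaccine Acceptance Survey and they are asked in the ED about booster receipt. All of this stands, and it limits the point to what could happen.

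A reader might also take the record-only rule for the secondary outcome as proof that the primary standard is too lax. It is not. A dose given in the study ED should be in that ED's record, whereas a dose given elsewhere may not be. A missing record does not show that the answer is false, and the phone call has a legitimate purpose. The ED comparison of M with Control does rest on the EHR, but it covers only index-visit doses and cannot stand in for a check on the 30-day outcome.

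Larger scenarios can be built. An excess of 10 points gives a bias of 3.6 to 5.4 points and a false-positive rate of 36–62%. That supposes excess false claims among those reached at twice the whole planned Control uptake, for which the documents offer no basis, so I do not rely on it.

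Finally, reopening a chart just found blank will often find nothing new, the phone form may already ask for date and place, and a recorded-doses-only analysis loses power. These are fair, and they shape the fix. What they leave unanswered is that no analysis by source is specified.

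**Conclusion.** The point holds in conditional form. An unverified phone answer has the same weight as a recorded dose, respondents are unblinded, only M is offered messaging, and the merged outcome cannot reveal over-reporting that differs by arm. If such a differential exists, the bias favours M. Under the assumed 40–60% reach and an excess of 2 to 5 points it is about 0.7 to 2.7 points, or roughly a tenth to two-fifths of the planned 7, with a two-sided false-positive rate of about 6.5% to 23% instead of 5%. Those figures rest wholly on assumed rates. Nothing here shows that the bias exists, that phone-only doses are false, or that the sample size is wrong. It is a cheap improvement worth making, not a defect that invalidates the primary outcome.

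**What to change.** Keep the EHR-or-phone definition of the primary outcome, because it captures doses given elsewhere. Then:

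1. In section XIII, code each positive as EHR-recorded or phone-only. For phone-only positives, record date and place if the phone form does not already ask for them, and have the blinded coordinator re-check the EHR immunization record for that specific dose. The yield may be modest, but it can recover late or overlooked entries.
2. In section XV, tabulate outcome source, phone consent and phone reach by arm.
3. In section XV, pre-specify for Aims I and III a sensitivity analysis that counts only record-confirmed doses. Phone-only positives are set to not vaccinated whether or not a date and place were given, since a plausible date is not verification. Report its estimate and 95% confidence interval beside the primary result.

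The cost is at most a few form fields, a second look at a chart already opened, and one further model run per aim. The sample size does not change. The downside is that the sensitivity analysis misses true outside doses and has less power (about 0.70 or 0.57 if the EHR captures 80% or 60% of doses). State in advance that it will be read by whether the direction and size of the effect are consistent with the primary result, not by whether significance survives.
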